10.7 Appendix 7: Pharmacogenomic Analysis With Banked Sample

INTRODUCTION

PGx research aims to provide information regarding how naturally occurring differences in a participant's gene and/or expression of genes based on genetic variation may impact what treatment options are best suited for the participant. Through investigation of PGx by technologies such as genotyping, gene sequencing, statistical genetics and Genome-Wide Association studies, the relationship between gene profiles and a drug's kinetics, efficacy, toxicity or disease may be better understood. As many diseases may be influenced by one or more genetic variations, PGx research may identify which genes are involved in determining the way a participant may or may not respond to a drug.

OBJECTIVES

The PGx research that may be conducted in the future with acquired blood samples is exploratory. The objective of this research will be to analyze or determine genes of relevance to clinical response, pharmacokinetics and/or toxicity/safety and/or disease.

By analyzing genetic variations, it may be possible to predict an individual participant's response to treatment in terms of efficacy and/or toxicity and/or disease.

PARTICIPANT PARTICIPATION

Participants who have consented to participate in this study will participate in the PGx substudy. Participants must provide written consent prior to providing any blood samples that may be used at a later time for PGx analysis.

SAMPLE COLLECTION AND STORAGE

Participants who consent to participate in this substudy will provide approximately 4 mL sample of whole blood/buccal swab per Astellas' instructions. Each sample will be identified by the unique participant number. Samples will be shipped to a designated banking CRO as directed by Astellas.

PGx ANALYSIS

Details on the potential PGx analysis cannot be established yet. Astellas may initiate the PGx analysis if evidence suggests that genetic variants may be influencing the drug's pharmacokinetics, efficacy and/or safety and/or disease.

DISPOSAL OF PGx SAMPLES/DATA

All PGx samples collected will be stored for a period of up to 15 years following study database lock. If there is no requirement for analysis, the whole blood sample will be destroyed after the planned storage period. The participant has the right to withdraw consent at any time. When a participant's withdraw notification is received, the PGx sample will be destroyed. The results of any PGx analysis conducted on a sample prior to its withdrawal will be retained at Astellas indefinitely unless otherwise specified by local regulation.

INFORMATION DISCLOSURE TO THE PARTICIPANTS

Exploratory PGx analysis may be conducted following the conclusion of the study, if applicable. The results of the PGx analysis will not be provided to any investigators or participants, nor can the results be requested at a later date. Any information that is obtained from the PGx analysis will be the property of Astellas.

10.8 Appendix 8: Infusion Reaction Dose Modification and Treatment (Guidelines for ASP7517 and Pembrolizumab)

Table 15 Infusion Reaction Dose Modification and Treatment (Guidelines for ASP7517 and Pembrolizumab)

NCI CTCAE Grade	Treatment	Premedication at Subsequent Dosing
Grade 1 Mild reaction; infusion interruption not indicated; intervention not indicated	
Increase monitoring of vital signs as medically indicated until the participant is deemed medically stable in the opinion of the investigator.	None
Grade 2 Requires therapy or infusion interruption but responds promptly to symptomatic treatment (e.g., antihistamines, NSAIDs, narcotics, intravenous fluids); prophylactic medications indicated for ≤ 24 h.	
Stop Infusion.Additional appropriate medical therapy may include but is not limited to:
Intravenous fluidsAntihistaminesNSAIDsAcetaminophenNarcoticsIncrease monitoring of vital signs as medically indicated until the participant is deemed medically stable in the opinion of the investigator.If symptoms resolve within 1 h of stopping drug infusion, the infusion may be restarted at 50% of the original infusion rate (e.g., from 100 mL/h. to 50 mL/h). Otherwise, dosing will be held until symptoms resolve and the participant should be premedicated for the next scheduled dose. 
Participants who develop grade 2 toxicity despite adequate premedication should be permanently discontinued from further study drug treatment (pembrolizumab only)
	
Pembrolizumab only: Participant may be premedicated 1.5 h (± 30 min) prior to infusion of pembrolizumab with:
 
Diphenhydramine 50 mg po (or equivalent dose of antihistamine).
 
Acetaminophen 500 to 1000 mg po (or equivalent dose of analgesic).
 
Contact the study medical monitor regarding ASP7517 dose management

Table continued on next page

NCI CTCAE Grade	Treatment	Premedication at Subsequent Dosing
Grades 3 or 4 Grade 3: Prolonged (i.e., not rapidly responsive to symptomatic medication and/or brief interruption of infusion); recurrence of symptoms following initial improvement; hospitalization indicated for other clinical sequelae (e.g., renal impairment, pulmonary infiltrates) Grade 4: Life-threatening; pressor or ventilator support indicated	
Stop Infusion.Additional appropriate medical therapy may include, but is not limited to:
Epinephrine*Intravenous fluidsAntihistaminesNSAIDsAcetaminophenNarcoticsOxygenPressorsCorticosteroidsIncrease monitoring of vital signs as medically indicated until the participant is deemed medically stable in the opinion of the investigator.Once the participant has been stabilized, collect blood for cytokine/chemokine panel (ad hoc collection for shipment to central lab).If the reaction is suggestive of anaphylaxis, collect blood (standard red top tube) for serum total tryptase level (levels typically peak within 3 h after the onset of symptoms). Serum should be frozen if the assay cannot be performed promptly at the local laboratory.Hospitalization may be indicated. 
* In cases of anaphylaxis, epinephrine should be used immediately. Participant is permanently discontinued from further study drug treatment.
	Any grade 4 hypersensitivity reaction/anaphylaxis, study treatment should be discontinued

Appropriate resuscitation equipment should be available at the bedside and a physician readily available during the period of drug administration. For further information, please refer to the Common Terminology Criteria for Adverse Events v5.0 (CTCAE) at <http://ctep.cancer.gov>.

NCI: National Cancer Institute; NSAID: non-steroidal anti-inflammatory drug

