4.1.4.1 ASP7517 Monotherapy Arm DLTs

- Non-hematologic AEs that are \geq grade 3 and that do not resolve to \leq grade 2 within 72 hours of onset
- Confirmed Hy's law case
- IRR that requires the infusion to be discontinued
- Prolonged delay (> 2 weeks) in initiating Cycle 2 due to treatment-related toxicity
- Any treatment-related toxicity that causes the participant to discontinue treatment during Cycle 1
- Grade ≥ 3 thrombocytopenia accompanied by bleeding that requires transfusion or hospitalization
- Grade ≥ 3 anemia requiring transfusion
- Grade 3 febrile neutropenia with or without infection
- Grade 5 treatment-related toxicity

The following AEs will not be considered as DLTs in the ASP7517 monotherapy arm:

- Electrolyte abnormalities that are not associated with clinical sequelae or deemed not clinically significant and corrected with appropriate management or supplementation within 72 hours of onset
- Grade 3 infusion site reaction if successfully managed and resolved within 72 hours
- Alopecia, anorexia or fatigue
- Grade 3 nausea and/or vomiting if not requiring tube feeding or total parenteral nutrition, or diarrhea and/or constipation if not requiring or prolonging hospitalization that can be managed to grade ≤ 2 with standard antiemetic or antidiarrheal medications used at prescribed dose within 72 hours of onset
- Grade 3 liver function test (LFT) elevations that resolve to \leq grade 1 within 7 days; LFT elevations lasting > 7 days that are considered to be clinically significant and at least possibly related to ASP7517 will be considered to be a DLT
- Grade 3 irAEs that resolve to \leq grade 1 within 72 hours of onset

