6.5 Dose Modification

Dose modifications of ASP7517 are not allowed at the individual participant level without prior consultation with the sponsor's medical monitor. Any participants who do not receive a subsequent dose within the scheduled time window in the schedules of assessments [[Table 1](#) and [Table 2](#)] can only resume treatment after discussion with the medical monitor. Any participant experiencing a grade 3 treatment-related AE after receiving a dose of ASP7517 may receive the subsequent scheduled dose of ASP7517 only after the observed grade 3 treatment-related AE has resolved to grade 1; the subsequent dose of ASP7517 may be reduced to a dose level deemed safe by the DESC. Further treatment reduction/withdrawal can be implemented after discussion with the medical monitor, including for any clinically significant AEs affecting vital organs (e.g., cardiac events).

Refer to the appendices and approved pembrolizumab package insert, summary of product characteristics monograph or local product information supplied by the manufacturer for the recommended treatment modifications for pembrolizumab.

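### For a Grade 3 ASP7517 infusion reaction, Table 15 and Section 6.5 do not give one instruction on stopping or re-dosing; in one narrow case this also leaves DLT status open

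*Protocol*

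**What the plan says.** Four parts of the protocol bear on a Grade 3 reaction to ASP7517.

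- **Section 10.8 (Appendix 8), Table 15, Grades 3 or 4 row, treatment column.** The title names both products. The instruction is "Stop Infusion", followed by supportive measures. At the end, directly after an asterisked note on epinephrine in anaphylaxis, comes "Participant is permanently discontinued from further study drug treatment". No product is named.
- **Same row, last column** (headed as premedication at subsequent dosing): "Any grade 4 hypersensitivity reaction/anaphylaxis, study treatment should be discontinued". Grade 3 is not mentioned.
- **Section 6.5.** A participant with a grade 3 treatment-related event after ASP7517 "may receive the subsequent scheduled dose of ASP7517 only after the observed grade 3 treatment-related AE has resolved to grade 1". Infusion reactions are not excepted. The section sends sites to the appendices for pembrolizumab modifications only.
- **DLT lists (synopsis, Sections 4.1.4.1 and 4.1.4.2).** Both arms list "IRR that requires the infusion to be discontinued" and, separately, "Any treatment-related toxicity that causes the participant to discontinue treatment during Cycle 1". Both also count a non-hematological event of grade 3 or higher that has not come down to grade 2 or lower within 72 hours. The text after the combination list lets a participant with a DLT continue ASP7517 if there is clinical benefit, the event has resolved and the sponsor has been consulted.

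The Grade 2 row of Table 15 is a useful contrast. There, "the infusion may be restarted at 50% of the original infusion rate" if symptoms settle within an hour, and the discontinuation sentence carries a product limit: the participant "should be permanently discontinued from further study drug treatment (pembrolizumab only". ASP7517 decisions at Grade 2 go to the medical monitor. The Grades 3 or 4 row has no restart provision, no product limit and no referral to the medical monitor.

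**The concern.** A site facing a Grade 3 ASP7517 infusion reaction must know whether the participant may be dosed again. Table 15 can be read as a permanent stop, while Section 6.5 permits another dose after recovery. Section 2.3.2 points to Appendix 8 for managing infusion reactions, but neither it nor Section 6.5 ranks the two rules. The list of mandatory discontinuation reasons in Section 8.1 has no infusion-reaction entry. The SAP does not help, since Sections 5.2.1.2 and 5.2.1.3 refer back to the protocol for DLTs.

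The first thing at stake is consistent handling of a safety-relevant decision across about 30 sites. The second is the DLT count. One DLT criterion is met by discontinuing treatment in Cycle 1, so the passage a site follows can become part of the toxicity outcome. Each arm expects only about 9 to 12 DLT-evaluable participants.

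**Working it through.** **1. The texts side by side for a Grade 3 ASP7517 reaction**

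| Text | If the Table 15 sentence covers the whole row | If it covers anaphylaxis only |
|---|---|---|
| Table 15, treatment column | Permanent discontinuation | Permanent discontinuation for anaphylaxis; silent for other reactions |
| Table 15, last column | Grade 4 only | Grade 4 only |
| Section 6.5 | Next dose permitted after resolution to grade 1 | Same |

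On the first reading the conflict covers every Grade 3 reaction. On the second it shrinks to Grade 3 anaphylaxis but does not vanish. For other Grade 3 reactions the site still cannot tell which reading is meant.

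**2. Infusion time** (Section 6.1.1: about 50 mL at 4 to 6 mL/min)

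Time = volume / rate: 50/6 = 8.3 min and 50/4 = 12.5 min. A reaction can therefore start when no infusion is left to stop. In escalation, participants are observed for at least 4 hours after dosing (Section 4.1.5.1).

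**3. When the choice decides DLT status** (related Grade 3 reaction)

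1. Onset during the Cycle 1 infusion: Table 15 stops the infusion and gives no restart at this grade, so the discontinued-infusion criterion is met under either rule. DLT both ways.
2. Not at grade 2 or lower within 72 hours: the 72-hour criterion is met. DLT both ways.
3. Cycle 1, onset after the infusion ends, grade 2 or lower within 72 hours: a DLT if treatment is discontinued in Cycle 1. If the participant stays on treatment, not a DLT unless another criterion applies.
4. Onset after the 28-day window: not a DLT either way.

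Only case 3 depends on the choice.

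**4. The BOIN table reproduced**

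Inputs: target φ = 0.30 (synopsis; SAP Section 6.5.1). Assumed, because the documents do not state them: φ1 = 0.6φ = 0.18, φ2 = 1.4φ = 0.42, and stopping when Pr(DLT rate > 0.30) exceeds 0.95 under a Beta(1,1) prior.

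- Escalation limit = ln[(1−φ1)/(1−φ)] / ln[φ(1−φ1)/(φ1(1−φ))] = ln(0.82/0.70) / ln(0.246/0.126) = 0.2365
- De-escalation limit = ln[(1−φ)/(1−φ2)] / ln[φ2(1−φ)/(φ(1−φ2))] = ln(0.70/0.58) / ln(0.294/0.174) = 0.3585

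These agree with the printed interval (0.236, 0.359), and every printed action for n = 3 to 8 reproduces.

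**5. Effect of one additional DLT on the printed action**

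| n | Action changes | Action does not change |
|---|---|---|
| 3 | 0→1 escalate to stay; 1→2 stay to de-escalate; 2→3 de-escalate to stop | none |
| 4 | the same three changes | 3→4 |
| 5 | 1→2 escalate to de-escalate; 3→4 de-escalate to stop | 0→1, 2→3, 4→5 |
| 6 | 1→2 escalate to stay; 2→3 stay to de-escalate; 3→4 de-escalate to stop | 0→1, 4→5, 5→6 |
| 7 and 8 | 1→2 escalate to stay; 2→3 stay to de-escalate; 4→5 de-escalate to stop | 0→1, 3→4, 5 and above |

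At n = 6, moving from one DLT to two takes the raw rate from 1/6 = 0.167 to 2/6 = 0.333, across the 0.30 ceiling in the MTD definition. That ceiling applies to the isotonic estimate, which equals the raw rate when the observed rates do not fall as dose rises.

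**The case against.** The strongest reply has four parts.

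- **The sentence may be part of the anaphylaxis note.** This is fair: it follows the asterisk directly, and its scope cannot be settled from the text. A reader might infer that Table 15 plainly bars re-dosing after every Grade 3 reaction. The documents do not support that as certain. The narrow reading still leaves Grade 3 anaphylaxis treated differently in three places.
- **The last column does not say that Grade 3 may continue.** This is correct. It names Grade 4 and sits under a premedication heading. It limits nothing expressly, but its silence on Grade 3 adds to the doubt about the sentence in the treatment column.
- **Section 6.5 is permissive.** It sets a minimum condition for the next dose and also allows withdrawal after discussion with the medical monitor, so a site that discontinues breaches nothing. That is true, but a site that re-doses under Section 6.5 may breach Table 15. A permission and a permanent stop cannot both apply to the same participant.
- **The Dose Escalation and Safety Committee confirms DLTs.** It does, but the criterion it would apply in case 3 asks whether treatment was discontinued. Review does not remove the dependence on what the site did.

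A reader might also infer that reactions after the infusion are common. The documents give no onset distribution for ASP7517, and Section 2.3.1.6 says infusion reactions were not seen nonclinically. The short infusion shows only that late onset is possible.

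**Conclusion.** The inconsistency stands. For a Grade 3 ASP7517 infusion reaction the protocol lacks one clear instruction on stopping or re-dosing, and under either reading of Table 15 at least Grade 3 anaphylaxis is handled inconsistently.

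The DLT consequence is real but narrow. It would be tempting to say that the choice of rule decides whether a Grade 3 reaction is a DLT. It does not in general, because only case 3 turns on it. Nor does every reclassified event alter the dose decision: 0/3 to 1/3 and 1/6 to 2/6 move from escalate to stay, while 0/6 to 1/6 remains escalate.

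This rests on reading the stop instruction at Grade 3 as ending the infusion, since a restart is offered only at Grade 2. If it were read as a temporary stop, more reactions would depend on the choice. It also treats the monotherapy exclusion for infusion site reactions as a different term from infusion-related reaction. Sample size, power and type I error are unaffected. The point ranks below must-fix, and no view is taken on which clinical rule is right.

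**What to change.** - In Table 15, state the scope of the discontinuation sentence by product and by grade, and say whether it covers the whole row or anaphylaxis only. Bring the last column into line.
- Reconcile this with Section 6.5 and with the post-DLT continuation text in Section 4.1.4.2 (repeated in the synopsis), so that one instruction applies to a Grade 3 ASP7517 infusion reaction. The sponsor's clinical team decides which rule stands.
- Make the DLT lists in the synopsis and Sections 4.1.4.1 and 4.1.4.2 consistent with that instruction.
- Check Table 18 at the same time, since it places the same sentence after its own anaphylaxis note for pembrolizumab.

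The cost is protocol wording in these places, with no change to the design or to any calculation. SAP Section 5.1.1 records early closure of the study. If dosing has ended, the clinical study report should state which rule was applied to any Grade 3 infusion reaction and whether each was counted as a DLT.

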10.9 Appendix 9: Monitoring of Pembrolizumab Potential Immune-related Adverse Events

Table 16 Monitoring of Pembrolizumab Potential Immune-related Adverse Events

Potential irAE	Closely monitor participants' symptoms for prompt diagnosis and management.
Pneumonitis	New cough, worsening cough, shortness of breath, or chest pain
Colitis	Changes in bowel habits; abdominal pain; blood or mucus in stool; nausea
Hepatitis	Yellowing of skin or whites of eyes; pain on right side of abdomen; dark urine (color of tea); nausea or vomiting; bleeding or bruising more easily than usual; loss of appetite; drowsiness
Endocrinopathies	Persistent or unusual headaches, changes in vision, rapid heartbeat, increased sweating, feeling very tired or weak, achy muscles, change in weight (gain or loss), feeling lightheaded or feeling faint, feeling more hungry or thirsty than usual, loss of hair, mood changes such as reduced sex drive or increased irritability, forgetfulness, feeling cold, constipation, deeper voice, urinating more frequently than usual, nausea or vomiting, abdominal pain
Motor/sensory neuropathy; Encephalitis; Myasthenic syndrome/myasthenic gravis or Guillain-Barre syndrome	Numbness or tingling, weakness, confusion, headache, forgetfulness, changes in mood or behavior, fever, increased sensitivity to light, neck stiffness
Ocular Inflammation	Changes in vision (blurry vision; double vision; other vision changes), eye pain, eye redness, eyelid swelling
Pancreatitis	Nausea or vomiting, abdominal pain
Infection	Fever, other signs of infection
Musculoskeletal inflammation	New or worsening joint symptoms, muscle weakness or pain

irAE: immune-related adverse event

10.10 Appendix 10: Dose Modification and Toxicity Management for Immune-related AEs

AEs associated with pembrolizumab exposure may represent an immune-related response. These irAEs may occur shortly after the first dose or several months after the last dose of pembrolizumab treatment and may affect more than one body system simultaneously. Therefore, early recognition and initiation of treatment is critical to reduce complications. Based on existing clinical study data, most irAEs were reversible and could be managed with interruptions of pembrolizumab, administration of corticosteroids and/or other supportive care. For suspected irAEs, ensure adequate evaluation to confirm etiology or exclude other causes. Additional procedures or tests such as bronchoscopy, endoscopy, skin biopsy may be included as part of the evaluation. Dose modification and toxicity management guidelines for irAEs associated with pembrolizumab are provided in Table 17.

Based on the mechanism of action of ASP7517, immune-related adverse reactions (e.g., fever, headache, fatigue, hot flashes, diarrhea and muscular and joint pain) should be considered (see [Section 2.3.1.8 Other]) and managed as required per standard of care. In case of such events, ensure adequate evaluation to confirm etiology or exclude other causes. In addition, the study medical monitor should be contacted to discuss event monitoring, follow up and study treatment management.

Table 17 Dose Modification and Toxicity Management Guidelines for Immune-related Adverse Events Associated with Pembrolizumab

General instructions:

1. Severe and life-threatening immune-related adverse events (irAEs) should be treated with intravenous corticosteroids followed by oral steroids. Other immunosuppressive treatment should begin if the irAEs are not controlled by corticosteroids.
2. Pembrolizumab must be permanently discontinued if the irAE does not resolve or the corticosteroid dose is not ≤ 10 mg/day within 12 weeks of the last pembrolizumab treatment.
3. The corticosteroid taper should begin when the irAE is \leq Grade 1 and continue at least 4 weeks.
4. If pembrolizumab has been withheld, pembrolizumab may resume after the irAE decreased to \leq Grade 1 after corticosteroid taper.

Table continued on next page

irAEs	Toxicity grade (CTCAE v5.0)	Action with pembrolizumab	Corticosteroid and/or other therapies	Monitoring and follow-up
Pneumonitis	Grade 2	Withhold	
 Administer corticosteroids (initial dose of 1 to 2 mg/kg prednisone or equivalent) followed by taper Add prophylactic antibiotics for opportunistic infections 	
 Monitor participants for signs and symptoms of pneumonitis Evaluate participants with suspected pneumonitis with radiographic imaging and initiate corticosteroid treatment
	Recurrent Grade 2, Grade 3 or 4	Permanently discontinue		
Diarrhea/Colitis	Grade 2 or 3	Withhold	
 Administer corticosteroids (initial dose of 1 to 2 mg/kg prednisone or equivalent) followed by taper 	
 Monitor participants for signs and symptoms of enterocolitis (i.e., diarrhea, abdominal pain, blood or mucus in stool with or without fever) and of bowel perforation (i.e., peritoneal signs and ileus) Participants with \geq Grade 2 diarrhea suspecting colitis should consider GI consultation and performing endoscopy to rule out colitis Participants with diarrhea/colitis should be advised to drink liberal quantities of clear fluids. If sufficient oral fluid intake is not feasible, fluid and electrolytes should be substituted via IV infusion
	Recurrent Grade 3 or Grade 4	Permanently discontinue		

Table continued on next page

irAEs	Toxicity grade (CTCAE v5.0)	Action with pembrolizumab	Corticosteroid and/or other therapies	Monitoring and follow-up
AST or ALT elevation or Increased Bilirubin	Grade 2 ^a	Withhold	
 Administer corticosteroids (initial dose of 0.5 to 1 mg/kg prednisone or equivalent) followed by taper 	
 Monitor with liver function tests (consider weekly or more frequently until liver enzyme value returned to baseline or is stable)
	Grade 3 ^b or 4 ^c	Permanently discontinue	
 Administer corticosteroids (initial dose of 1 to 2 mg/kg prednisone or equivalent) followed by taper 	
Type 1 diabetes mellitus (T1DM) or Hyperglycemia	New onset T1DM or Grade 3 or 4 hyperglycemia associated with evidence of β-cell failure	Withhold ^d	
 Initiate insulin replacement therapy for participants with T1DM Administer anti-hyperglycemic in participants with hyperglycemia 	
 Monitor participants for hyperglycemia or other signs and symptoms of diabetes
Hypophysitis	Grade 2	Withhold	
 Administer corticosteroids and initiate hormonal replacements as clinically indicated 	
 Monitor for signs and symptoms of hypophysitis (including hypopituitarism and adrenal insufficiency)
	Grade 3 or 4	Withhold or permanently discontinue ^d		
Hyperthyroidism	Grade 2	Continue	
 Treat with non-selective beta-blockers (e.g., propranolol) or thionamides, as appropriate 	
 Monitor for signs and symptoms of thyroid disorders
	Grade 3 or 4	Withhold or permanently discontinue ^d		
Hypothyroidism	Grade 2, 3, 4	Continue	
 Initiate thyroid replacement hormones (e.g., levothyroxine or liothyronine) per standard of care 	
 Monitor for signs and symptoms of thyroid disorders

Table continued on next page

Footnotes

irAEs	Toxicity grade (CTCAE v5.0)	Action with pembrolizumab	Corticosteroid and/or other therapies	Monitoring and follow-up
Nephritis: grading according to increased creatinine or acute kidney injury	Grade 2	Withhold	
 Administer corticosteroids (prednisone 1 to 2 mg/kg or equivalent) followed by taper 	
 Monitor changes of renal function
	Grade 3 or 4	Permanently discontinue		
Myocarditis	Grade 1 or 2	Withhold	
 Based on severity of AE administer corticosteroids 	
 Ensure adequate evaluation to confirm etiology and/or exclude other causes
	Grade 3 or 4	Permanently discontinue		
All Other immune-related AEs	Persistent Grade 2	Withhold	
 Based on severity of AE administer corticosteroids 	
 Ensure adequate evaluation to confirm etiology or exclude other causes
	Grade 3	Withhold or discontinue based on the event ^c		
	Recurrent Grade 3 or Grade 4	Permanently discontinue		

^a AST/ALT: > 3.0 - 5.0 × ULN if baseline normal; > 3.0 - 5.0 × baseline, if baseline abnormal;
 bilirubin: > 1.5 - 3.0 × ULN if baseline normal; > 1.5 - 3.0 × baseline if baseline abnormal

^b AST/ALT: > 5.0 to 20.0 × ULN, if baseline normal; > 5.0 - 20.0 × baseline, if baseline abnormal; bilirubin: > 3.0 - 10.0 × ULN if baseline normal; > 3.0 - 10.0 × baseline if baseline abnormal

^c AST/ALT: > 20.0 × ULN, if baseline normal; > 20.0 × baseline, if baseline abnormal;
 bilirubin: > 10.0 × ULN if baseline normal; > 10.0 × baseline if baseline abnormal

^d The decision to withhold or permanently discontinue pembrolizumab is at the discretion of the investigator or treating physician. If control achieved or ≤ Grade 2, pembrolizumab may be resumed.

^e Events that require discontinuation include but are not limited to: Guillain-Barre Syndrome, encephalitis, Stevens-Johnson Syndrome and toxic epidermal necrolysis.

AE: adverse event; ALT: alanine aminotransferase; AST: aspartate aminotransferase; CTCAE: common terminology criteria for adverse events; GI: gastrointestinal; irAE: immune-related adverse event; ULN: upper limit of normal

10.11 Appendix 11: Dose Modification and Toxicity Management of Infusion Reactions Related to Pembrolizumab

Pembrolizumab may cause severe or life-threatening infusion-reactions including severe hypersensitivity or anaphylaxis. Signs and symptoms usually develop during or shortly after drug infusion and generally resolve completely within 24 hours of completion of infusion. Dose modification and toxicity management guidelines on pembrolizumab associated infusion reaction are provided in Table 18.

Table 18 Pembrolizumab Infusion Reaction Dose Modification and Treatment Guidelines

NCI-CTCAE Grade	Treatment	Premedication at Subsequent Dosing
Grade 1 Mild reaction; infusion interruption not indicated; intervention not indicated	
Increase monitoring of vital signs as medically indicated until the participant is deemed medically stable in the opinion of the investigator.	None
Grade 2 Requires therapy or infusion interruption but responds promptly to symptomatic treatment (e.g., antihistamines, NSAIDs, narcotics, IV fluids); prophylactic medications indicated for ≤ 24 h.	
Stop Infusion.Additional appropriate medical therapy may include but is not limited to:IV fluidsAntihistaminesNSAIDsAcetaminophenNarcoticsIncrease monitoring of vital signs as medically indicated until the participant is deemed medically stable in the opinion of the investigator.If symptoms resolve within 1 h of stopping drug infusion, the infusion may be restarted at 50% of the original infusion rate (e.g., from 100 mL/h. to 50 mL/h). Otherwise dosing will be held until symptoms resolve and the participant should be premedicated for the next scheduled dose. 
Participants who develop Grade 2 toxicity despite adequate premedication should be permanently discontinued from further study drug treatment
	Participant may be premedicated 1.5 h (± 30 min) prior to infusion of pembrolizumab with: Diphenhydramine 50 mg po (or equivalent dose of antihistamine). Acetaminophen 500 to 1000 mg po (or equivalent dose of analgesic).

Table continued on next page

NCI-CTCAE Grade	Treatment	Premedication at Subsequent Dosing
Grades 3 or 4 Grade 3: Prolonged (i.e., not rapidly responsive to symptomatic medication and/or brief interruption of infusion); recurrence of symptoms following initial improvement; hospitalization indicated for other clinical sequelae (e.g., renal impairment, pulmonary infiltrates) Grade 4: Life-threatening; pressor or ventilator support indicated	
• Stop Infusion.• Additional appropriate medical therapy may include but is not limited to:
• Epinephrine†• IV fluids• Antihistamines• NSAIDs• Acetaminophen• Narcotics• Oxygen• Pressors• Corticosteroids• Increase monitoring of vital signs as medically indicated until the participant is deemed medically stable in the opinion of the investigator.• Hospitalization may be indicated. 
†In cases of anaphylaxis, epinephrine should be used immediately. Participant is permanently discontinued from further study drug treatment.
	

Appropriate resuscitation equipment should be available at the bedside and a physician readily available during the period of drug administration. For further information, please refer to the Common Terminology Criteria for Adverse Events v5.0 (CTCAE) at <http://ctep.cancer.gov>

NCI: National Cancer Institute; NSAID: nonsteroidal anti-inflammatory drug

